## LIST OF ABBREVIATIONS

ACCORD	Academic and Clinical Central Office for Research & Development - Joint office for The University of Edinburgh and Lothian Health Board
ADHD	Attention deficit hyperactivity disorder
BOLD	Blood oxygen level dependent
CI	Chief investigator
CpG	Cytosine-phosphate-guanine (5'—C— phosphate —G—3')
CRF	Case report form
CRP	C-reactive protein
DNAm	DNA methylation
EoP	Encephalopathy of prematurity
FA	Fractional anisotropy
GA	Gestational age
GCP	Good Clinical Practice
HC	Hierarchical complexity
HIPAA	Health Insurance Portability and Accountability Act
HPA	Hypothalamic-pituitary-adrenal
ICH	International Conference on Harmonisation
ICVF	intracellular volume fraction of water
IQ	Intelligence quotient
LC-MS/MS	Liquid chromatography tandem mass spectrometry
MD	Mean diffusivity
MRI	Magnetic resonance imaging
MSN	Morphometric similarity network
MTsat	Magnetisation transfer imaging
NDI	Neurite density index
NICU	Neonatal intensive care unit
NNRD	National Neonatal Research Database
NODDI	Neurite orientation dispersion and density imaging

NPD	National Pupil Database
ODI	Orientation dispersion index
PAG	Parental advisory group
PI	Principal investigator
PSMD	Peak-width skeletonised
PTB	Preterm birth
PTB-RF	Preterm birth-associated risk factor
QA	Quality assurance
REC	Research Ethics Committee
RT-PCR	Reverse transcription polymerase chain reaction
SAIL	Secure Anonymised Information Linkage
ScotXeD	Scottish Exchange of Data
SEN	Special Edu
SES	Socioeconomic status
(S)IMD	(Scottish) Index of Multiple Deprivation
SLC	Speech, language or communication
SOP	Standard Operating Procedure
SQA	Scottish Qualifications Authority
TEBC	Theirworld Edinburgh Birth Cohort

# 1 INTRODUCTION

## 1.1 BACKGROUND

Globally, preterm birth (PTB), defined as birth at less than 37 weeks of gestation, affects 15 million pregnancies per annum, with country prevalence between 5 and 18%. Over the past two decades, the survival rate of children born preterm has improved due to advances in perinatal medicine but outcomes remain challenging: 10-15% of children born very preterm (<32 weeks) develop cerebral palsy, 30-50% develop an intellectual disability, and this population is at increased risk of problems with socialisation, behaviour, language, low educational attainment, autism, and attention deficit hyperactivity disorder. Adults who were born preterm are more likely to experience a mood disorder, age-related cognitive impairment, schizophrenia, and cardiometabolic disease. PTB accounts for one of the highest numbers of disability-adjusted life years of any single childhood condition. **There are no effective treatments for improving brain health after preterm birth, which brings into sharp focus the need to identify protective factors and intervention targets.**

The neurobiological basis for adverse neurological, cognitive and psychiatric outcomes following preterm birth is related to cerebral white matter injury and subsequent dysmaturational processes in white matter and neuroaxonal structures collectively termed the ‘encephalopathy of prematurity’ (EoP). With features of EoP apparent on magnetic resonance imaging (MRI), this has become an important assessment modality for investigating determinants of brain health in preterm infants.

**Our premise, based on studies showing that adverse outcomes are not inevitable, is that it is not PTB per se that has a deleterious effect on brain development but rather, it is multiple, often interacting PTB-associated risk factors (PTB-RFs).** These are biological, psychosocial, and social/infrastructural, and can affect parent or child, or be shared, for instance: maternal/infant stress, infection/inflammation, suboptimal infant nutrition, co-morbidities of PTB, and socioeconomic deprivation (Figure 1).

[figure not shown]

Figure 1. PTB-associated risk factors linked with altered cognition in children, proposed biological pathways that transmit risk to atypical brain development/outcome, and image biomarkers for delineating upstream pathways and predicting risk and resilience

## 1.2 RATIONALE FOR STUDY

To intervene against the negative effects of PTB on child development requires a quantitative understanding of PTB as a complex multi-dimensional risk exposure and new knowledge about *how* PTB-RFs modify brain development.

**1.2.1 The perinatal stress environment and outcomes after preterm birth:** Prenatal exposure to maternal stress affects 10–35% of children worldwide and is associated with adverse neuropsychiatric outcomes. Adaptation of the maternal hypothalamic-pituitary-adrenal (HPA) axis with consequent variation in transfer of glucocorticoids to the developing fetus appears to be a key mechanism linking maternal stress to offspring neurodevelopment.

Our recent studies suggest this could be an important axis for embedding PTB-RFs in brain development. First, maternal hair cortisol concentrations during pregnancy are associated with newborn amygdala architecture across the whole GA range, indicating that HPA axis activation links the prenatal stress environment to a key neural substrate of socioemotional development in childhood. Second, alterations in placental expression of genes regulating cortisol regeneration and placental transfer consistent with increased fetal glucocorticoid exposure occur in association with lower maternal socioeconomic status. Third, maternal consumption of glycyrrhizin (a potent inhibitor of placental 11 $\beta$ -hydroxysteroid dehydrogenase type 2, the "barrier" to maternal glucocorticoids), is associated with adverse neurodevelopmental and neuropsychiatric outcomes in children. Fourth, extremely preterm infants (<28 weeks) tend to have blunted cortisol reactivity to vaccination at 4 months, suggesting low GA (or a co-exposure such as repeated painful experiences during neonatal intensive care) programmes HPA axis adaptation. Fifth, neonatal hair glucocorticoids are a marker of both prenatal and postnatal physiological stressors in preterm infants. Finally, chronic HPA axis activation is a plausible mechanistic link between early life stress, altered brain morphology and major depression in adulthood. Based on these studies, we propose that atypical HPA axis activity is triggered by PTB-RFs and is an axis through which multidimensional exposures become embedded in the brain development of preterm infants.

**1.2.2 Systemic inflammation and encephalopathy of prematurity:** Early studies revealed that neurodevelopmental outcomes are worse if infants are exposed to co-morbidities of preterm birth characterised by systemic inflammation, for example, chorioamnionitis, bloodstream infection, and necrotising enterocolitis. This is because inflammation alters oligodendrocyte precursor responses, increases proliferation and death, and impairs maturation into myelin-forming oligodendrocytes. The consequent hypomyelination deprives axons of metabolic/trophic support and insulation for electrical impulse conduction, resulting in EoP.

Emerging evidence indicates that PTB is associated with sustained inflammation. Specific mediators of the adaptive and immune responses to preterm birth and its co-morbidities have been linked to MRI features of EoP; however, there are inconsistencies in the broader literature associating inflammation with neurodevelopment, in part, because of the absence of standard peripheral biomarkers of low-level systemic chronic inflammation in neonates, and partly because study designs have relied on a single (or low frequency) measurement of selected proteins that are highly phasic, maturation-dependent, and subject to swift and rapid concentration changes in plasma. There are no effective markers of low-level systemic chronic inflammation. We propose that DNA methylation (DNAm) profiles may provide a more accurate reflection of inflammatory exposure. This assertion is based on three key observations: specific DNAm profiles exist in inflammatory diseases, they predict levels of inflammatory proteins and neuroinflammation-related outcomes including brain structure and cognition in children and adults, and DNAm proxies have greater longitudinal stability and stronger associations with cognition than serum measures. These observations are of particular interest because age- and birth weight- related differences in DNAm are present across a large number of CpGs. Recently, we have shown that PTB is associated with profound and widely distributed changes in the methylome (saliva), and these are linked to MRI features of EoP.

**1.2.3 Neural mechanisms of cognitive development in children born preterm:** The neuroprofile of preterm children includes atypical social cognition, attention, memory, and language. An open question is the extent to which these phenotypes are domain-specific, or whether domain-general traits underpin these challenges. For example, resolving whether social difficulties are due to reduced ability

to reason about other peoples' minds versus problems with different aspects of cognition - such as language or attention - is critical for developing mechanistically-informed interventions to promote social development. These alternative accounts cannot be distinguished behaviourally because both lead to impaired performance on behavioural tasks. Functional magnetic resonance imaging (fMRI), however, has potential to clarify the cognitive and neural mechanisms of impairments because different brain regions support different cognitive processes. Continuing the exemplar of social cognition, adults and children recruit a network of brain regions when engaging in social reasoning including bilateral temporal parietal junction (TPJ), precuneus, and medial prefrontal cortex. We have shown that this network becomes increasingly functionally specialised during early childhood and that children who perform better on behavioural Theory of Mind tasks, an indicator of reasoning about others' minds, have more functionally mature, selective responses in the right TPJ and more correlated activity between brain regions within this cortical network. If children born preterm have domain-specific atypicalities in social cognition, these atypicalities should be accompanied by atypical development in social brain regions.

Recent fMRI studies provide evidence for early disruptions in functional connectivity (measured during rest) in infants born preterm^41 and, importantly, early functional connectivity in preterm infants predicts motor and cognitive outcomes at age two and can be promoted with interventions (e.g., playing music during neonatal care). To our knowledge, there have not been task-based fMRI studies of cognition in early childhood (i.e., ages 2-5 years) following preterm birth, in part because of methodological challenges of carrying out fMRI in young children. We have shown that fMRI is feasible with children as young as three years old with the use of strategies that prepare children for MRI scans and child-friendly movie-viewing fMRI experiments, and that movie-viewing fMRI experiments provide a particularly sensitive neural marker of individual differences in cognition, relative to measures collected during rest. In preparation for this application, we secured a Wellcome Trust Institutional Strategic Support Fund award to set-up task-based fMRI in 5-year-olds, so we are ready to implement the protocols in our proposed study.

**Elucidation of the pathways that link PTB-RFs with abnormal brain development and outcome is essential for developing neuroprotective strategies based on re-programming stress response systems, immunomodulation, and cognitive training.**

## Hypotheses

Work package 1:

1) Specific preterm birth associated risk factors (PTB-RFs), which may be clinical/demographic, psychosocial (e.g. maternal stress), or social/infrastructural (e.g. deprivation), modify the relationship between GA at birth and neurodevelopmental and/or educational outcomes

Work package 2:

2i) Atypical activation of the HPA axis leads to EoP, indexed on MRI by dysmaturity (altered chronological brain age), reduced connectome complexity, and biomarkers of hypomyelination

2ii) DNAm proxies of chronic systemic inflammation are present in preterm infants at term equivalent age and are associated with MRI features of EoP.

2iii) The effect of PTB-RFs identified in WP1 on brain development are mediated by alterations in the neonatal HPA axis and/or chronic systemic inflammation.

Work package 3:

3i) Preterm children have domain-specific delays in cognition at school age

3ii) Structure-function networks underpinning cognition are altered in preterm children

3iii) PTB-RFs identified in WP1 predict structural and functional maturity at 5-years

This protocol describes a programme of work packages. Permissions and approvals for each work package will be managed separately. New approvals will be sought for WP1 which will be led and managed by investigators based at Imperial College London. New approvals will also be sought for WP2 which will be led and managed by investigators based at the University of Edinburgh. WP3 already has approvals in place and is managed by University of Edinburgh investigators (Research Ethics

Committee No: 16/SS/0154, NHS Lothian R&D No: 2016/0255). Permissions are not required for WP4. Detailed information about these arrangements can be found in section 12.1 Ethical Conduct.

## 2 STUDY OBJECTIVES

### 2.1 OBJECTIVES

The overarching aim of this programme is to determine the biological, psychosocial and socioeconomic PTB-RFs that lead to adverse neurodevelopmental, cognitive, and educational outcomes in children born preterm and to identify the neuroendocrine and epigenetic axes that embed these risks in brain development. This aim will be met through 5 objectives:

2.1.1. Investigate the contributions of multidimensional PTB-RFs to neurodevelopmental and educational outcomes of children born preterm. We will create novel linkages between the National Neonatal Research Database, which contains routine data for ~100,000 infants born in the UK with gestational age (GA) <32 weeks between 01/01/2008-31/12/2019, with education records and neighbourhood deprivation indices. This will determine the relative contributions of demographic, clinical and socioeconomic PTB-RFs to neurodevelopmental and educational outcomes of British children.

2.1.2. Identify the biological axes underlying abnormal brain development in preterm infants. We will characterise brain dysmaturation associated with PTB using neonatal magnetic resonance imaging and use this to investigate the relationship between a) Hypothalamic pituitary-adrenal (HPA) axis activity, and; b) low-level chronic, systemic inflammation indexed by DNA methylation (DNAm), and brain development.

2.1.3. Identify the neural substrates associated with impaired cognitive and behavioural outcomes of preterm children at school age. We will use multiple neuroimaging modalities to identify structural and functional brain networks that predict outcomes (e.g., social development, attention) at 5 years. The contribution of potentially modifiable factors to childhood outcomes, including PTB-RFs identified in the first objective, will be investigated.

2.1.4. Identify neural markers to assess efficacy in future trials of neuroprotective therapies. Our studies linking HPA axis activity, DNAm markers of inflammation and quantitative MRI measures of brain development with outcomes will provide imaging biomarkers that can be used to design and test the efficacy of potential treatments in future studies.

2.1.5. Involve parents and survivors of preterm birth in research. We will engage and involve parents and advocacy groups (e.g., the Adult Premie Advocacy Network) to guide the design, delivery and dissemination of the programme and to plan follow-on work that arises from it. We will appoint a virtual parental advisory group (PAG) of 6-8 parents together. The PAG will co-design parent and public-facing materials and advise on dissemination plans. We will commission an artist to work with the PAG to develop pictorial/visual/animated ways of communicating.

We will with the public engagement officer at the MRC CRH, [name], to run engagement events that may include:

- Co-ordinated patient information days to support current patients and their support networks
- Panel events at Science Festivals combining experts and past patients/parents of patients, a policy maker (Member of Scottish Parliament), and a health journalist.
- Awareness raising initiatives inviting target audiences, such as Instagram Lives (via UoE Medical School), Twitter Q&A, a MRC Festival event.
- The creation of a scientific animation to illustrate the subject, research insights, and offer accessible and digestible information to families requiring further support.
- Influencing Policy makers: Invite MP/MSP to learn more about our research into Preterm Birth and the possible outcomes, and how families can be better supported.
- Participation in the University of Edinburgh public lecture series.

## 2.2 ENDPOINTS

The programme is organised in 4 work packages, each with specific endpoints:

### 2.1.1 Endpoint WP1

We will define, at population level, the weighted contributions of multidimensional PTB-RFs to neurodevelopmental outcomes and real-world educational performance of children born preterm. Identifying the role of societal as well as clinical/demographic factors could be of particular importance to resource-poor settings.

### 2.1.2 Endpoint WP2

We will identify targets in neuroendocrine stress and immune pathways that lead to atypical brain development, and elucidate the PTB-RFs that activate those pathways.

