## **6 STUDY ASSESSMENTS**

### **6.1 STUDY ASSESSMENTS**

**WP1:** Not applicable.

**WP2:** See Table 1.

**WP3:** See Table 2.

Table 1. WP2 assessments

Data collection point	Age	Data collection method	Sample type / domain	Test / task	Time implication for participants	Notes
1	Antenatal	administrative /electronic records & interview	Medical, deomgraphic, SES	Ethnic background and language spoken at home; parents' education and employment; family income; family structure, housing, neighbourhood quality, parents' mental health, social network and support  History and exposures: life events, prescribed medications, alcohol, smoking, substances, pregnancy complications	45 mins	
2	Birth	administrative /electronic records, questionnaire & tissue	Medical	Peripartum history and exposures, mother and infant Anthropometry	30 mins	
			Placenta	Structured histopathology rating and storage mRNA levels of glucocorticoid related genes	n/a	Collect and store
			Umbilical cord blood	i) 2ml umbilical cord blood; ii) dried blood spot for storage	n/a - sampling linked to clinical episodes	i) Endogenous glucocorticoids and metabolites (glucocorticoid release); glucocorticoid receptor in cord blood leukocytes (glucocorticoid signalling). ii) Inflammatory markers and DNA (collect and store)
			Hair, infant	Overall glucocorticoid secretion	15 mins	
			Hair, maternal	Overall glucocorticoid secretion	15 mins	
		Saliva	Methylome	10 mins	Term controls	
3	Neonatal	tissue	Dried blood spot	Inflammatory markers and DNA	n/a - sampling linked to clinical episodes	Collect and store
		tissue	Saliva	Methylome	10 mins	Preterms at term equivalent age
		tissue	Hair, infant	Overall glucocorticoid secretion	15 minutes	Preterms at term equivalent age
		biosample	Faeces	Microbiome	n/a	Collect and store: early (7-14 days) stool (cases and controls) and pre-discharge (cases)
		administrative /electronic records & direct observation	Medical	Anthropometry	n/a - linked to clinical episodes	
			Co-morbidities and exposures	Co-morbidities of preterm birth, medications, feed type and method; health status of control group.	n/a - sampling linked to clinical episodes	
			Parent IQ	National Adult Reading Test	15 mins	
		MRI	Brain structure and connectivity	sMRI, dMRI	90 minutes	Morphometric similarity networks, hierarchical complexity, magnetisation transfer imaging
		administrative /electronic records & questionnaire	Demographics & medical	Update perinatal history	15mins	

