equivalent age (*overall glucocorticoid secretion*). Sample collection will conform to an SOP, and analysis will use published, validated methods for measuring metabolites from hair and blood at the UoE Clinical Research Facility Mass Spectrometry Core . The 5-year saliva cortisol samples (on waking, 30 minutes after waking and bed-time) are being collected as part of the TEBC protocol.

**DNAm.** Saliva DNAm will be sampled from preterm infants at term equivalent age to reflect the allostatic load of perinatal inflammation. Saliva will be collected in Oragene OG-575 Assisted Collection kits, by DNA Genotek, and according to an SOP. DNAm analysis using the Illumina Human MethylationEPIC BeadChip is established in the Edinburgh Clinical Research Facility Genetics Core.

**Questionnaire and records.** Demographic and clinical information will be extracted from the maternal and infant record by a member of the research team. The tools to assess cognition, behaviour, well-being and family circumstances are listed in Tables 1 and 2. Hard copies will be stored securely in locked filing cabinets in a locked room to which only study researchers have access.

The programme manager will oversee data collection, ensuring that time-points are adhered to for each participant. Participants will be contacted by post and / or telephone to arrange appointments and to prompt if questionnaires have not been returned, to maximise completeness of data collection.

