We will apply machine learning methods including feature selection and statistical mapping algorithms. Indicatively, we will use both filter feature selection approaches and embedded feature selection, e.g. the random forest feature importance scores to determine the most parsimonious model comprising a robust feature subset with maximally predictive performance using standard model validation approaches (e.g. k-fold cross-validation). We have previously shown that this approach determines predictors of language impairment in preterm infants with high accuracy. Here, we envisage it will determine the PTB-RFs that jointly contribute, in descending order of importance, to neurodevelopment and educational outcome measures. We will apply partial dependence plots to gain further insights into how specific changes in variable values affect outcomes, and we will explore two-dimensional data representations (e.g., applying t-distributed stochastic neighbour embedding) to visualize data both using the original high-dimensional space and using feature subsets determined using feature selection algorithms. This approach will provide a clear demonstration of the effect of PTB-RFs inherently as part of the statistical model used, including direction of effect as a function of different outcome values, thus accounting for mediation.

**WP2.** Image processing will be carried out using established pipelines for morphometric similarity networks (MSNs), hierarchical complexity (HC) and using in-house techniques for MTsat. There are two statistical approaches. The first will use multivariate statistics in a predictive framework to test whether PTB-RFs are associated with MSNs (brain age), HC (connectome architecture), and MTsat (a marker of myelination). The second will use mediation analyses within a structural equation modelling framework to investigate the role of neuroendocrine stress activation and chronic inflammation as mediators of PTB-RFs on features of EoP. This simultaneously characterises associations among HPA axis activation/DNAm, PTB-RFs, and brain features, and specifically tests the hypothesis that stress and/or chronic inflammation partly and significantly mediate associations between PTB-RFs and brain development.

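### For the preterm DNAm score and the term-equivalent hair, WP2 cannot tell mediation from reverse or shared causation, yet the endpoint and mediation claims are worded as causal

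*Protocol*

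**What the plan says.** **Claims.** The Protocol's Endpoint WP2 reads: "We will identify targets in neuroendocrine stress and immune pathways that lead to atypical brain development". Under Hypotheses, 2i says "Atypical activation of the HPA axis leads to EoP". Hypothesis 2iii says the effects of the risk factors identified in WP1 "are mediated by alterations in the neonatal HPA axis and/or chronic systemic inflammation". Section 9.2 (WP2) plans mediation analysis in a structural equation model (SEM) that "specifically tests the hypothesis that stress and/or chronic inflammation partly and significantly mediate associations between PTB-RFs and brain development". Hypothesis 2ii is more cautious and claims only association: "DNAm proxies of chronic systemic inflammation are present in preterm infants at term equivalent age and are associated with MRI features of EoP".

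**Sampling.** Section 7 says: "Saliva DNAm will be sampled from preterm infants at term equivalent age to reflect the allostatic load of perinatal inflammation". In Table 1 (section 6.1), saliva at birth is for term controls. The neonatal saliva and the second infant hair sample carry the note "Preterms at term equivalent age" and sit in data collection point 3. The MRI row ("Brain structure and connectivity") is in the same data collection point, with no age and no order relative to the samples. Section 6.2 ends WP2 assessments at timepoint 3. Dried blood spots are to be collected and stored, and section 6.3 makes their analysis subject to funding.

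**Earlier HPA measures.** Table 1 and section 7 also place cord-blood glucocorticoids, the leukocyte glucocorticoid receptor, and maternal and infant hair at birth, which is before the MRI.

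**The concern.** A mediation claim needs the mediator to act on the outcome. For the inflammation arm in preterm infants, the mediator is a single score from the same data collection point as the MRI. The term-equivalent hair is in the same position. The score is meant to sum up inflammation since before birth, and the MRI phenotype also sums up development over that interval, so nothing in the schedule orders the mediator-to-outcome leg.

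The wording nevertheless moves from association in 2ii to mediation in 2iii and section 9.2, and to targets in the endpoint, using that same sample. A significant indirect effect could then be presented as an immune or stress target for treatment when it reflects a consequence of brain injury, or illness severity acting on both. Objective 2.1.4 intends these links to inform the design and testing of future therapies, so the causal reading would be used.

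**Working it through.** There is no figure in the plan to reproduce: section 9.1 gives no alpha, power or path size for the WP2 mediation. The check has two parts.

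**1. Can model fit decide the direction?** Let X be a risk factor, M the mediator and Y the MRI measure. A partial-mediation model has three paths (X to M, X to Y, M to Y) and three correlations to explain, so it has 3 − 3 = 0 degrees of freedom and fits perfectly. Reversing the last arrow gives the same count and the same perfect fit. Direction has to come from the design, and for these two mediators the design does not supply it.

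**2. How often would mediation be declared with no effect of M on Y?** The setting is n=200, the planned preterm group, because term controls give saliva at birth and not at point 3. Variables are standardised. Mediation is declared when X to M, and M to Y given X, are each significant at two-sided .05 and the product has the sign of the total effect. There are 4,000 simulated studies per setting. All path sizes are assumed.

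*Reverse causation (X to Y, then Y to M):*

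| X to Y | Y to M | mediation declared |
|---|---|---|
| .2 | .2 | 6% |
| .3 | .3 | 25% |
| .4 | .4 | 62% |
| .5 | .4 | 81% |

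*Unmeasured shared cause C (X to C, then C to both M and Y):*

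| X to C | C to M and C to Y | mediation declared |
|---|---|---|
| .2 | .5 | 26% |
| .4 | .4 | 31% |
| .3 | .5 | 51% |
| .4 | .5 | 71% |
| .5 | .6 | 98% |

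When M and Y have no link beyond X, both paths are significant in about 5% of studies (sign ignored).

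**Apparent size of the false indirect effect.** The M-to-Y slope given X is b = (r_MY − r_XM·r_XY)/(1 − r_XM²), and the indirect effect is r_XM·b.

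- Reverse causation at .3/.3: r_XM = .3 × .3 = .09, r_XY = .3, r_MY = .3. Then b = (.3 − .027)/(1 − .0081) = .275, the indirect effect is .09 × .275 = .0248, and .0248/.3 = 8% of the total effect appears mediated.
- Shared cause at .4/.5: r_XM = r_XY = .4 × .5 = .2, r_MY = .5 × .5 = .25. Then b = (.25 − .04)/(1 − .04) = .219, the indirect effect is .0438, and .0438/.2 = 22% appears mediated.

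**What the proposed sensitivity output would show.** The residual correlation that brings the indirect effect to zero is the partial correlation of M and Y given X, (r_MY − r_XM·r_XY)/√[(1 − r_XM²)(1 − r_XY²)]. It is .273/√(.9919 × .91) = .29 in the first example and .21/.96 = .22 in the second. A reader could then judge whether residual severity might plausibly produce a correlation of that size.

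**The case against.** Several points on the other side are sound.

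- **A shared data point does not mean the same moment.** Point 3 covers the whole neonatal window, including stool at 7 to 14 days and pre-discharge stool. Full imaging details are in a published paper cited by section 7 and not available here. A reader might infer that saliva and scan are simultaneous. The documents show only that their order is not stated. Even saliva taken shortly before the scan would reflect largely the same interval.
- **The neuroendocrine arm has earlier measures.** A reader might infer that the whole WP2 endpoint lacks time order. It does not: cord blood and birth hair precede the MRI.
- **The measures are meant to look backward.** Section 7 describes DNAm as cumulative load and hair as overall secretion. Section 1.2.2 argues that inflammation impairs myelination, and nothing in the protocol proposes that brain change drives a salivary score. This weakens the reverse-causation reading without removing it, and leaves the shared-severity reading untouched.
- **Shared severity is confounding, not timing.** Earlier sampling does not cure it, and birth measures can be confounded too. WP2 does collect co-morbidities, medications and peripartum exposures, so adjustment is possible. The simulation assumes none.
- **Confounder sets and sensitivity models often belong in a SAP, which may exist.** Their absence is therefore not the point. The point is the endpoint and hypothesis wording set against the sampling schedule, both of which this protocol fixes.
- **Section 9.2 is partly cautious.** It speaks of characterising associations, and the *lead to* wording is in the endpoint and 2i, not in 2iii. Even so, 2iii and 9.2 do claim mediation.

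**Conclusion.** The concern holds for the preterm DNAm score and the term-equivalent infant hair. For these, a significant indirect effect in the planned SEM cannot be distinguished from reverse or shared causation, and the endpoint, 2iii and section 9.2 claim more than 2ii does from the same sample. It holds much less for the HPA axis measured at birth, where time order exists and confounding is the remaining issue.

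The size is illustrative. At n=200, mediation is declared falsely in about 6% to 81% of studies under reverse causation and 26% to 98% under an unmeasured shared cause. These ranges depend wholly on assumed paths, complete data and no adjustment for severity. They do not show that false mediation will be reported, only that the risk can be large and that the design cannot detect it. Because the remedy needs no new data, this is a cheap improvement that changes what WP2 can conclude.

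**What to change.** 1. In Endpoint WP2, hypothesis 2iii and section 9.2, word results for the DNAm score and the term-equivalent hair as associated with MRI features, or consistent with mediation. Do not describe them as pathways that lead to abnormal development or as targets.
2. Rest any time-ordered mediation claim on the birth HPA measures (cord blood, maternal and infant hair at birth).
3. Keep the planned SEM, including the DNAm paths, so that the inflammation half of 2iii is still examined. Adjust the mediator-MRI path for the illness-severity data already collected: co-morbidities, medications and peripartum exposures.
4. Beside every indirect effect, including those through birth measures, report the residual mediator-MRI correlation that would bring it to zero.

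The cost is wording in three places, covariates already in the dataset and one more sensitivity output, with no new visits or samples. The downside is a weaker headline claim for inflammation.
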